14.2.2 Clinical Status

Clinical status will be based on data collected on the ‘Ordinal Scale for Clinical Status’ eCRF page and is assessed with the following ordinal scale:

0. Uninfected: no clinical or virological evidence of infection.
1. Ambulatory: no limitation of activities.
2. Ambulatory: limitation of activities.
3. Hospitalized, mild disease: hospitalized, no oxygen therapy.
4. Hospitalized, mild disease: oxygen by mask or nasal prongs.
5. Hospitalized, severe disease: noninvasive ventilation or high-flow oxygen.
6. Hospitalized, severe disease: intubation and mechanical ventilation.
7. Hospitalized, severe disease: ventilation + additional organ support – e.g., pressors, RRT, ECMO
8. Death.

In case of death, the participant will be counted with the clinical status =8 (death) for any scheduled timepoint after death date. There will be no imputation of missing data.

Clinical status is expected every day during hospitalization and then at every scheduled visit after discharge. Day 1 assessment will serve as baseline measurement. If missing, the last non-missing measurement prior to randomization will be used.

The number and percentage of participants in each clinical status category as well as summary statistics for absolute and change from baseline status will be presented by treatment group, in a tabular and graphical form, using a stacked bar chart.

A cumulative logit model will be used to compare the clinical status results of each M5049 group versus placebo at the following analysis visits: Day 7, Day 14, Day 21, Day 28, Day 44 and Day 60 according to the ordinal scale described above. Under the assumption of proportional odds, the odds ratio (OR) and its 95% Wald CI will be estimated for each M5049 group versus placebo. A score test for the proportional odds assumptions will be reported.

Should the model fail, due to an insufficient number of observations per category of the dependent variable, then relevant categories may be collapsed.

In addition, the following dichotomized versions of the clinical status will be derived, only if at least 6 participants in each level are present:

- Death (clinical status = 8) versus any other category (clinical status \neq 8)
- Worsening (clinical status \geq 5) versus stable/improvement (clinical status $<$ 5)
- In-hospital (clinical status \geq 3) versus hospital discharged (clinical status $<$ 3).

A logistic regression model will be used to compare the dichotomized version of the clinical status at each time point of interest, with terms for treatment arm and strata defined by randomization strata. The OR and its 95% Wald CI will be estimated for each M5049 group versus placebo.

The same logistic regression model will be used to analyze the clinical status deterioration (change from baseline $>$ 0) versus stable/improvement (change from baseline \leq 0) compared to baseline.

No multiplicity correction will be applied.

14.2.3 Time to SpO₂ ≥ 94% sustained for at least 24 hours in room air from Day 1 through Day 28

Time to SpO₂ ≥ 94% sustained for at least 24 hours in room air will be based on data collected on the 'Pulse Oximetry' and 'Respiratory Status' eCRF pages from Day 1 through Day 28.

The time to SpO₂ improvement, defined as the time from first dose (Day 1) to the date of first SpO₂ ≥ 94% sustained in room air, in days:

- Time to SpO₂ improvement (days) = (Date/time of first SpO₂ ≥ 94% sustained in room air – Date/time of first dose)

The rules for the different types of censoring below will be followed:

| # | Description | Date of Event or Censoring | Outcome |
|---|---|----------------------------|----------|
| 1 | Death from Day 1 up to D60/Study completion | D28 | Censored |
| 2 | Failure at any point and time during the study from D1 up to D28, defined as: * ICU admission leading to treatment discontinuation * use of mechanical ventilation * relapse | D28 | Censored |

| | | | |
|---|---|---|----------|
| 3 | Participant not confirmed to be eligible based on inclusion criterion 6 (PDEV05 code) | Date of first dose of study drug | Censored |
| 4 | No post-baseline SpO2 data | Date of first dose of study drug | Censored |
| 5 | Sustained SpO2 \geq 94% at room air before Day 28 | Date of first SpO2 \geq 94% sustained at room air | Event |
| 6 | SpO2 $<$ 94% at room air through Day 28 without death or failure | D28 | Censored |
| 7 | Early discontinuation before or on Day 28 without improvement, failure or death | Date/time of last available result of clinical status from Day 1 through Day 28 | Censored |

Of note, the endpoint will not be considered met if the assessment is not done at room air, irrespective from the actual SpO2 value.

Number and percentage of subjects with and without improvement will be presented.

The hypotheses that will be tested for each dose level using a one-sided stratified log-rank test of distribution of time to improvement with use of corticosteroids at a prednisone equivalent daily dosage of \leq 15 mg or $>$ 15 mg within 48 hours prior to randomization, and country as stratification factors, are:

- H_{0i} : $HR_i \leq 1$
- H_{1i} : $HR_i > 1$

where

- HR_i denotes the Hazard Ratio of M5049 dose i versus placebo
- i denotes M5049 50 mg BID or M5049 100 mg BID
- $HR_i > 1$ denotes an improvement compared to placebo.

Estimation of the effect of each treatment dose (and 95% two-sided CI) separately compared to placebo will be based on hazard ratio from stratified Cox-model of improvement hazard rate, with terms for treatment group (each active treatment separately against placebo), use of corticosteroids

at a prednisone equivalent daily dosage of ≤ 15 mg or > 15 mg within 48 hours prior to randomization, and country. Ties will be handled using the discrete method.

Cumulative distribution function for time to improvement will be estimated via Kaplan-Meier (product limit) method by treatment group and presented together with associated statistics (median time to improvement, improvement rates at Day 7, Day 14, Day 21 and Day 28) including the corresponding two-sided 95% CI. The estimates of the standard error (SE) will be computed using Greenwood’s formula.

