6.1.5 Preparation

M5049 film-coated tablets and placebo film-coated tablets are ready for oral use. No special handling is required unless the participant is unable to receive study intervention by mouth.

For those participants who cannot take the tablets by mouth during Part B of the study, e.g., participants who are mechanically intubated, refer to the Pharmacy Manual for information on preparation of the tablets (study intervention) and application via an NGT. Participants in Part A of the study will need to discontinue study intervention if/when they are no longer able to take tablets by mouth.

7 Measures to Minimize Bias: Randomization and Blinding

Once the participant meets inclusion and exclusion criteria, the Investigator or delegate will request the blinded study intervention treatment assignment using the IWRS. The study will randomize participants 1:1:1 to M5049 50 mg, M5049 100 mg, or placebo twice daily.

Part A participants will be stratified by presence/absence of obstructive lung disease. Part B participants will be stratified based on (1) the use of corticosteroids at a prednisone equivalent daily dosage of ≤ 15 mg or > 15 mg within 48 hours prior to randomization, (2) the use of antiviral therapy including convalescent plasma (presence or absence) within 48 hours prior to randomization, and (3) country.

Participant numbers will be assigned in the appropriate format and will reflect study number, site number and participant identification. Participant numbers will not be reassigned to other participants or reused in this study. If a participant is replaced, the replacement will be enrolled with a unique participant number.

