10.4.3.2 Analysis of Clinical Status

The number and percentage of participants in each clinical status category will be presented by treatment group and by time point in a graphical manner.

An ordinal logistic regression model will be used to compare the clinical status from Day 1 through Day 60 of M5049 groups to placebo. Under the assumption of proportional odds, a summary odds ratio and its 95% CI will be estimated for each M5049 group versus placebo. A test for the proportionality assumption will also be made.

Separate odds ratios will also be estimated for dichotomized version of the health status:

- Death versus any other category.
- Worsening versus stable/improvement.
- Not discharge versus hospital discharged.

An exploratory longitudinal analysis will be run to account for all of the time points and present estimates of treatment effect by time point.

10.4.3.3 Analysis of Time to SpO₂ of $\geq 94\%$ Sustained for at Least 24 hours in Room Air

The time to response is defined as the time from first dose (Day 1) to the date of the first SpO₂ $\geq 94\%$ sustained for at least 24 hours in room air up to Day 28. For participants who die and those considered as failure (that includes use of mechanical ventilation, ICU admission leading to treatment discontinuation, and relapse) the time to response will be censored at Day 28. For participants completing the study without meeting response or failure, the time to response will be censored at Day 28. Participants withdrawn before the End of Study Visit without meeting response or failure will be censored at the last date of SpO₂ assessment in room air temperature.

Cumulative distribution function for time to response will be estimated via the Kaplan-Meier (product-limit estimates) method by treatment group and presented together with associated statistics (median time to response, response rates at Day 7, Day 14, and Day 28) including the corresponding two-sided 95% CI.

10.4.3.4 Analysis of All-cause Mortality Through Day 60

Number and percentage of death through Day 60 with 95% CI will be presented by treatment group.

10.4.3.5 Analysis of Time to Intensive Care Unit Admission (Day 1 Through Day 28)

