6.3 Final Analysis

This analysis will be the main analysis. All planned analyses identified in the study protocol and in this IAP will be performed only after the last participant has completed the safety follow up period with all study data in-house, and the database will be locked for the analysis.

A data review meeting will be held prior to any database lock.

7 Changes to the Planned Analyses in the Clinical Study Protocol

The inclusion of all stratification factors is identified as a potential source of problems in the implementation and interpretation of statistical models used to analyze efficacy. For this, use of corticosteroids before randomization and country will only be included, as deemed the most relevant factors, while presence of obstructive lung disease and use of antiviral therapy before randomization will be analyzed as subgroups.

8 Analysis Populations and Subgroups

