8.2 Subgroup Definition and Parameterization

The following factors, based on data collected on the eCRF, will be used as cofactors for all the stratified analyses:

- Treatment with corticosteroids therapy within 48 hours from randomization (as collected in the ‘Randomization’ eCRF page)
 - Corticosteroids dose \leq 15 mg of prednisone-equivalent (reference level)
 - Corticosteroids dose $>$ 15 mg of prednisone-equivalent

- Country
 - United States of America (reference level)
 - Philippines
 - Brazil

The following subgroups then, including the two stratification factors defined above and based on information collected at baseline, will be defined:

Comorbidities:

- Presence of obstructive lung disease (as collected in the ‘Medical History’ eCRF page)
 - No (reference level)
 - Yes

- Obesity based on BMI
 - No: Body Mass Index (BMI - derivation described at Section 11.1) $<$ 30 kg/m² (reference level)
 - Yes: BMI \geq 30 kg/m²

- Diabetes co-morbidity at study entry (as collected in the ‘Medical History’ eCRF page)
 - No (reference level)
 - Yes

- Heart diseases co-morbidity at study entry (as collected in the ‘Medical History’ eCRF page)
 - No (reference level)
 - Yes

- Hypertension co-morbidity at study entry (as collected in the ‘Medical History’ eCRF page)
 - No (reference level)
 - Yes

- Number of relevant comorbidities (derived for each participant counting the number of comorbidities among the ones listed above, including obesity based on BMI):
 - No (reference level)
 - Yes: 1 or 2
 - Yes: more than 2

Use of Relevant Therapies at baseline:

- Treatment with corticosteroids therapy within 48 hours from randomization (as collected in the 'Randomization' eCRF page)
 - Corticosteroids dose \leq 15 mg of prednisone-equivalent (reference level)
 - Corticosteroids dose $>$ 15 mg of prednisone-equivalent
- Treatment with antiviral therapy (AVT) including convalescent serum within 48 hours from randomization (as collected in the 'Randomization' eCRF page)
 - No (reference level)
 - Yes

Demographic characteristics:

- Age (derivation described at Section 11.1)
 - Age $<$ 60 (reference level)
 - Age \geq 60
- Gender
 - Male (reference level)
 - Female
- Ethnicity
 - Hispanic or Latino
 - Not Hispanic nor Latino (reference level)

Other characteristics:

- Country
 - United States of America (reference level)
 - Philippines
 - Brazil
- Site
- Smoking status at study entry (as collected in the ‘Substance Usage’ eCRF page)

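### The cumulative logit model for clinical status is described without the stratification terms that its companion models carry; its terms should be stated, with corticosteroid stratum, country and age included

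*SAP*

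**What the plan says.** SAP 14.2.2 sets out the ordinal analysis thus: "A cumulative logit model will be used to compare the clinical status results of each M5049 group versus placebo", at analysis Days 7, 14, 21, 28, 44 and 60. Under proportional odds, "the odds ratio (OR) and its 95% Wald CI will be estimated for each M5049 group versus placebo". A score test of the assumption follows, and categories may be collapsed if the fit fails. Treatment is the only term named. Protocol 10.4.3.2 names no covariate either: "An ordinal logistic regression model will be used to compare the clinical status from Day 1 through Day 60 of M5049 groups to placebo".

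The models around it do name their factors:
- The logistic models for dichotomised clinical status, in the same SAP section, are fitted "with terms for treatment arm and strata defined by randomization strata". The same model is used for deterioration from baseline.
- The Cox models in SAP 14.1.1, 14.2.3 and 14.2.5 carry corticosteroid use and country.
- The common difference in proportions in SAP 14.2.1 is stratified by the same two factors.

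Two general rules bear on the gap. On the efficacy models, SAP Section 7 says: "The inclusion of all stratification factors is identified as a potential source of problems in the implementation and interpretation of statistical models used to analyze". It then settles that "use of corticosteroids before randomization and country will only be included, as deemed the most relevant factors". SAP 8.2 says that these two factors "will be used as cofactors for all the stratified analyses". SAP 14.2.2 does not describe the cumulative logit model as stratified.

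On the design, Protocol Section 7 states: "Part B participants will be stratified based on (1) the use of corticosteroids at a prednisone equivalent daily dosage of". The cut lies at 15 mg, and antiviral therapy and country are the other two factors. Part A was stratified by obstructive lung disease alone.

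**The concern.** A programmer who follows SAP 14.2.2 literally fits treatment only. One who follows Section 7 adds two factors. The two fits give different odds ratios from the same data, and nothing in the visible text says which is intended, so the choice could end up being made after unblinding.

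If the literal reading is followed, there are two consequences. First, odds ratios are non-collapsible: leaving out a prognostic factor moves the odds ratio towards 1 even with perfect balance. The ordinal odds ratio would be marginal while the dichotomised ones beside it are conditional on strata, so a difference between them could reflect the conditioning rather than the cut of the scale. Second, when randomisation is balanced on strongly prognostic strata, a model that omits them overstates the standard error of the treatment effect, and its Wald test becomes conservative.

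**Working it through.** **Plan's own figure.** None can be reproduced. The protocol text of Section 10 before 10.3 is blacked out, and no power or precision figure for clinical status is visible.

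**Inputs from the documents.** 15 participants in Part A and 135 in Part B give 15 + 135 = 150 (Protocol 4.1). Allocation is 1:1:1, so 150/3 = 50 per arm. Tests are two-sided with 95% intervals (SAP Section 9).

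**Assumptions, not in the documents.**
- Placebo split over six collapsed Day 14 categories: 30/30/12/12/6/10%.
- 60% of participants above 15 mg prednisone-equivalent; countries 30/30/40%.
- One standardised, age-like continuous covariate.
- A true conditional odds ratio of 1 or 2 for one active arm, with the other active arm null.
- Log-odds effects for corticosteroid, country (plus or minus) and covariate (per SD): none 0; weak 0.3, 0.2, 0.25; moderate 0.6, 0.4, 0.5; strong 1.0, 0.7, 0.8.
- Permuted blocks within corticosteroid by country for all 150. This simplifies Part A.

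**Model.** logit P(Y ≤ k) = α_k + treatment, then + corticosteroid + country, then + age. Each scenario has 1,500 trials, fitted by maximum likelihood with a Wald test at 1.96.

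| Strength | Terms | Mean log OR | Mean SE | Power, OR 2 | Type I error, OR 1 |
|---|---|---|---|---|---|
| None | treatment | 0.699 | 0.369 | 47.9% | 5.4% |
| | + strata | 0.710 | 0.370 | 49.0% | 5.5% |
| | + age | 0.713 | 0.372 | 49.5% | 5.7% |
| Weak | treatment | 0.670 | 0.368 | 43.1% | 4.9% |
| | + strata | 0.687 | 0.370 | 45.1% | 5.7% |
| | + age | 0.697 | 0.373 | 46.0% | 5.3% |
| Moderate | treatment | 0.641 | 0.368 | 40.8% | 4.6% |
| | + strata | 0.677 | 0.372 | 43.8% | 5.8% |
| | + age | 0.716 | 0.378 | 46.2% | 5.9% |
| Strong | treatment | 0.573 | 0.367 | 34.1% | 3.6% |
| | + strata | 0.635 | 0.375 | 39.7% | 5.7% |
| | + age | 0.726 | 0.387 | 47.0% | 5.5% |

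Mean log OR, SE and power are for the true OR of 2, where log 2 = 0.693. Monte Carlo error is √(0.45 × 0.55/1500) = 1.3 points for power and √(0.05 × 0.95/1500) = 0.6 points for type I error. All three models see the same data, so differences between them are known more tightly.

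**Reading the table.**
- Power gain from strata: 1.1, 2.0, 3.0 and 5.6 points. With age: 1.6, 2.9, 5.4 and 12.9 points.
- The gain in the first scenario cannot be real, because nothing there is prognostic. It shows slight small-sample optimism in the larger models, which also overshoot 0.693 a little (0.726 at most).
- Attenuation: in the moderate case the exponentiated mean is e^0.641 = 1.90 unadjusted and e^0.716 = 2.05 with all terms; in the strong case, e^0.573 = 1.77 and e^0.726 = 2.07.
- The standard error does not fall. With all terms it rises by 0.372/0.369 − 1 = 0.8% (none) up to 0.387/0.367 − 1 = 5.4% (strong).
- In the strong case with OR 1, the unadjusted model's mean SE was 0.359 against an empirical SD of 0.341. This explains the 3.6% type I error.

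**The case against.** The best reply is that the SAP may already adjust this model. Section 7 speaks of the models used for efficacy in general and keeps two factors; clinical status is an efficacy endpoint. The contents list also shows a blacked-out entry between 14.2.2 and 14.2.3 that cannot be checked. This stands in part: a reader might infer that the SAP prescribes an unadjusted model, but the documents are silent rather than explicit. The silence still matters, because 8.2 ties the factors to stratified analyses and 14.2.2 names strata for the logistic models but not for this one.

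A reader might also infer that precision is given up at no cost. The working does not support that: the interval on the log-odds scale widens slightly, and the odds ratio becomes conditional. The SAP also has a stated reason to limit factors and foresees failure in sparse categories. Protocol 4.7 expects most participants to be discharged by Day 28, so Days 44 and 60 may fill few categories. These are reasons for a short list and a fallback. They are not reasons against the two factors that Section 7 itself retains.

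Two further limits stand. Corticosteroid use and country were not design strata for the 15 Part A participants, who are pooled with Part B. And no visible efficacy model uses age, so adding it is a recommendation and not a correction of an inconsistency. The case for it is that age is derived for participants in SAP 11.1, and the protocol's amendment rationale calls older participants a higher-risk group.

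Baseline ordinal score might seem the natural next covariate. Inclusion criteria 5 and 6 exclude ventilation and cap inspired oxygen, so the score is compressed at entry and need not be added.

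**Conclusion.** The point holds as a gap in specification with a modest statistical cost. As written, the cumulative logit model has treatment as its only term; its odds ratio is then marginal, attenuated if corticosteroid use, country or age is prognostic, and not comparable in kind with the stratum-adjusted odds ratios next to it.

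Under the assumed inputs at 50 per arm, the two factors are worth roughly 1 to 6 points of power and all three terms 2 to 13. The credible part is 2 to 3 points in the weak case, 3 to 5 in the moderate case and 6 to 13 in the strong case. Some of that gain is the adjusted test running slightly above 5% while the unadjusted one runs below. The figures depend on covariate strengths that the documents do not give.

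The documents do not support calling the planned analysis invalid. Omitting the terms does not inflate type I error here. The analysis is secondary, and SAP Section 9 treats every test as exploratory. The change is worth making because it is cheap and removes a choice that should be fixed before unblinding.

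**What to change.** In SAP 14.2.2:
- State that the cumulative logit model at each analysis visit includes treatment, corticosteroid stratum, country and age (continuous).
- Report the unadjusted odds ratio as supportive. Apply the existing collapsing rule first; if the adjusted model still fails at a visit, report the unadjusted odds ratio for that visit.
- Use the same terms and fallback in the logistic models of that section, so that all odds ratios condition on the same set. Replace the reference there to the randomisation strata with the two factors kept in Section 7. As main effects, the Part B strata take 1 + 1 + 2 = 4 parameters (corticosteroid, antiviral, country); the proposed terms also take 1 + 2 + 1 = 4.
- Say in one sentence that the adjusted odds ratio is conditional.
- Confirm that the corticosteroid category, which SAP 8.2 takes from the randomisation page of the eCRF, is available for Part A, and state how a missing value is handled.

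SAP 14.2.4, 14.2.12 and 14.2.13 still stratify by antiviral use; reconcile them with Section 7 in the same edit.

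The cost is a few sentences before database lock and negligible programming. The statistical price is the 0 to 5% rise in the standard error of the log odds ratio and a conditional rather than marginal estimate.

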4.1 Overall Design

This is a 2-part, Phase II double-blind, randomized, placebo-controlled study to evaluate the safety of and clinical response to M5049 tablets taken orally twice daily for 14 days in participants initially hospitalized because of moderate to severe COVID-19 pneumonia. Participants will be followed to assess those who are alive and not requiring supplemental oxygenation (including noninvasive or mechanical ventilation and ECMO) at Day 14 in the M5049 compared to placebo groups. Participants will continue to be followed to document their need for oxygen or ventilation support and clinical status through Day 28, and complete safety follow-up (and vital signs) through Day 60.

Eligible study participants, who test SARS-CoV-2 positive as established by local guidelines, will not be on mechanical ventilation and must have an SpO₂ < 94% in room air and partial pressure of oxygen (PaO₂)/fraction of inspired oxygen (FiO₂) ≥ 150 with a maximum FiO₂ 0.4.

Part A participants will be stratified by presence/absence of obstructive lung disease. Part B participants will be stratified based on (1) the use of corticosteroids at a prednisone equivalent daily dosage of ≤ 15 mg or > 15 mg within 48 hours prior to randomization, (2) the use of antiviral therapy including convalescent plasma (presence or absence) within 48 hours prior to randomization, and (3) country.

If the attending hospital physician anticipates the participant may require mechanical ventilation in the first 24 hours of entering in the study, the participant should not be approached for consent. Study participants should be provided the local standard/supportive care but cannot be on chloroquine-related medications or other immunomodulating drugs to enter the study (the exception is that if corticosteroids are initiated prior to or during the study Screening period [and prior to randomization], they are allowed but they must not be higher than 40 mg prednisone per day based on the dosing regimen and schedule used in the RECOVERY Trial (NCT04381936; [Horby 2020](#)). If the local standard of care includes use of an antiviral therapy (and/or convalescent plasma), which has been uniformly agreed to by the site, has the permission of the local Principal Investigator, and the Sponsor has been notified, participants on antiviral therapy may be eligible for enrollment.

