Participants will be randomized 1:1:1 to receive M5049 50 mg, M5049 100 mg, or placebo tablets orally twice daily (every 12 hours). Part A and Part B of this exploratory study will each consist of an up to 48-hour Screening Period, a 14-day treatment period at the start of the overarching 28-day inpatient and/or outpatient Surveillance period, and up to a 32-day inpatient and/or outpatient Safety Follow-up Period. Details of management of potential drug toxicity and study intervention discontinuation for the participant are provided in Section 8.1.

Part A of the study will pause enrollment after 15 participants have been randomized to the study-defined intervention (see Figure 1). Unless a participant is terminated from the study as a treatment failure or for safety reasons, and after consultation with the Sponsor, participants randomized in Part A may be replaced if they have discontinued the study before completing 14 days of treatment. An internal Independent Data Monitoring Committee (IDMC) that provides ongoing surveillance of participant safety will review available safety and clinical outcomes data and will provide a recommendation whether or not the study is safe to proceed to Part B. Details of the review may be found in the IDMC charter.

Part B of the study will enroll approximately 135 participants (see Figure 2). Detail analyses performed for the purpose of risk/benefit monitoring, the full membership, mandate, and processes of the IDMC may be found in the IDMC charter. The IDMC will decide whether or not to continue the study as per protocol or make recommendations as specified in the IDMC charter. Unless there is reason to halt the study based on IDMC recommendations, a total of 150 participants are planned to be randomized and followed in Part A and Part B of this study.

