11.1 Demographics

Demographic characteristics and physical measurements will be summarized descriptively using the following information from the ‘Demography’ and ‘Screening Vital Signs’ eCRF pages.

The following demographic characteristics will be included:

- Sex: male, female
- Race: white, black or African American, Asian/ Pacific Islander, American Indian or Alaska Native, more than one race, other, unknown
- Ethnic origin: Hispanic or Latino/Not Hispanic or Latino
- Age (years)
- Age categories:
 - < 60 years,
 - ≥ 60 years
- Country: Brazil, Philippines, United States of America
- Site
- Height (cm) at Baseline

- Weight (kg) at Baseline
- BMI (kg/m²) at Baseline
 - < 30 kg/m²,
 - ≥ 30 kg/m²

Specifications for computation:

- Age [years]
 - (date of given informed consent - date of birth + 1) / 365.25
 - In case of missing day for at least one date, but month and year available for both dates: For the derivation of age, the day of informed consent and the day of birth will be set to 1 and the formula above will be used
 - In case of missing month for at least one date, but year available for both dates: For the derivation of age, the day and the month of informed consent and the day and month of birth will be set to 1 and the formula above will be used

The integer part of the calculated age will be used for reporting purposes.

- BMI [kg/m²] = $\frac{\text{weight [kg]}}{\text{height[cm]}^2} \times 10000$

All demographic data will be reported in listings.

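### The dichotomised clinical-status models use logistic regression with Wald intervals from as few as 6 participants in a level and name no method for an arm without events; at 6 events over all arms the chance of such an arm is about 1 in 4

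*SAP*

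**What the plan says.** SAP 14.2.2 defines three binary versions of the 9-point scale: death against any other category, status 5 or higher against lower, and in hospital against discharged. The entry condition is that "dichotomized versions of the clinical status will be derived, only if at least 6 participants in each level are present". The text does not say whether the count is taken over the three arms together or within each arm.

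The analysis is then set out: "A logistic regression model will be used to compare the dichotomized version of the clinical status at each time point of interest". As to covariates, the SAP specifies a model "with terms for treatment arm and strata defined by randomization strata". For reporting, "The OR and its 95% Wald CI will be estimated for each M5049 group versus placebo". No penalised, exact or profile-likelihood method is named. The same model is also applied to deterioration (any increase from baseline), which is described afterwards and is not among the outcomes listed under the 6-participant condition.

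The section has one sparse-data provision, the collapsing of outcome categories. It follows the cumulative logit model, and a binary outcome has nothing left to collapse.

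On the model terms, SAP section 7 says that "use of corticosteroids before randomization and country will only be included, as deemed the most relevant factors". SAP 11.1 gives three countries: "Country: Brazil, Philippines, United States of America". Protocol 4.1 also lists among the Part B factors "the use of antiviral therapy including convalescent plasma (presence or absence) within 48 hours prior to randomization, and (3) country". SAP 14.2.2 refers only to randomization strata, without saying whether these enter as main effects or as crossed cells.

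**The concern.** With main effects, the model has five slopes: two for treatment, one for corticosteroids and two for country. The plan allows it to be fitted with as few as 6 participants in the rarer outcome level. If an arm has no participant in that level, the maximum-likelihood odds ratio for that arm lies on the boundary and its Wald interval cannot be used.

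Death and status 5 or worse are outcomes on which harm or benefit would be looked for. The threshold of 6 presents the model as estimable at counts where it may well not be. If it fails, the remedy would have to be chosen after the data are seen.

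**Working it through.** The documents give no event rate or zero-cell probability for these models, so there is no planned figure to reproduce.

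**Inputs.** Protocol 4.1 states that "a total of 150 participants are planned to be randomized" (15 in Part A plus 135 in Part B), allocated 1:1:1, so 50 per arm. The minimum count is 6 in the rarer level (SAP 14.2.2). Assumptions: the 6 is an overall count, risk is equal across arms, and no data are missing. The rarer level is called the event below.

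**Chance of an arm without events.** With *e* events among 150 participants, inclusion-exclusion on the hypergeometric distribution gives:

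- a named arm empty: C(100,e)/C(150,e)
- either arm of one dose-placebo pair empty: [2·C(100,e) − C(50,e)]/C(150,e)
- any of the three arms empty: [3·C(100,e) − 3·C(50,e)]/C(150,e)

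At e = 6, C(100,6)/C(150,6) = 0.0834 and C(50,6)/C(150,6) = 0.0011. Any arm empty is therefore 3 × (0.0834 − 0.0011) = 0.247. The multinomial approximation, 3(2/3)^6 − 3(1/3)^6 = 0.259, agrees closely.

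| Events, all arms | Any arm empty | Given dose-placebo pair affected | Placebo empty |
|---|---|---|---|
| 4 | 0.5465 | 0.3757 | 0.1935 |
| 5 | 0.3710 | 0.2509 | 0.1273 |
| 6 | 0.2468 | 0.1656 | 0.0834 |
| 7 | 0.1623 | 0.1085 | 0.0544 |
| 8 | 0.1059 | 0.0707 | 0.0354 |
| 10 | 0.0444 | 0.0296 | 0.0148 |

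The rows for 4 and 5 events matter only if the minimum does not cover the deterioration analysis.

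**If the doses reduce risk.** With assumed risk ratios against placebo, at 6 events (multinomial), the chance of an empty arm is 27.6% for 0.75/0.75, 35.5% for 0.5/0.5, 50.0% for 0.5/0.25 and 58.3% for 0.25/0.25.

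**What an empty stratum does.** The distribution over countries and corticosteroid levels is not in the documents, so a range was used. At 6 events, with main effects, the chance that some corticosteroid or country level has no event runs from 28.2% (equal levels) to 84.8% (country 70/20/10, corticosteroids 10/90). With six equal crossed cells, the chance of an empty cell is 98.5%.

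Logistic models were fitted to 3,000 simulated trials per setting, with 6 events, no treatment effect, and strata as main effects or crossed. The treatment odds ratio was 0 or infinite in 24–26% of trials in every setting, which matches the empty-arm rate. When a stratum was empty but no arm was, the treatment odds ratio stayed finite in 99.8–100% of trials. Only the stratum's own coefficient diverged.

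**Illustration, unadjusted, 50 per arm.**

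- 1 event on a dose against 3 on placebo: OR = (1/49)/(3/47) = 0.32, Wald interval 0.03 to 3.18.
- 0 against 3: OR = 0 with no usable Wald interval. Adding 0.5 to each cell, as a Firth-type fit does here, gives (0.5/50.5)/(3.5/47.5) = 0.13. The interval on that scale is 0.007 to 2.67.

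**The case against.** Several points on the other side stand.

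- **The risk is concentrated at the bare minimum.** It falls below 5% by 10 events. The documents give no event rates, so nobody can say how often a count of 6 or 7 would arise. Status 5 or worse and in-hospital both include death, so their counts are at least the death count.
- **The count may be per arm.** If the 6 applies within each arm, no arm can be empty under the rule. The overall count is the more natural reading of a condition on outcome levels, but the text does not settle it.
- **The same outcomes are shown in other ways.** Every category is tabulated and plotted by arm. Mortality has Wilson intervals (SAP 14.2.4), and ventilation or death has Kaplan-Meier and log-rank analyses (SAP 14.2.6 and 14.2.7). The backup for deaths is incomplete at the threshold: the Miettinen-Nurminen difference, which tolerates a zero cell, needs more than 6 deaths through Day 60, while the logistic model needs only 6.
- **The stakes are limited.** SAP section 9 treats all tests as exploratory, and an odds ratio of 0 or infinity is conspicuous rather than silently wrong. A Firth-type interval of 0.007 to 2.67 is computable but tells the reader little.
- **The visible text is not the whole section.** The contents list shows a redacted entry between 14.2.2 and 14.2.3, so the absence of a separation method can be asserted only for what is shown.

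A reader might infer the stronger claim that an unusable odds ratio is more likely than not at 6 events, by counting empty strata with empty arms. The chance that some arm or factor level is empty is indeed 46.8% with equal levels and up to 89% with the most uneven mix tried. That does not measure harm to the reported result, because the plan reports the treatment odds ratio and an empty stratum leaves it finite. Under equal risk the figure is about 1 in 4; it reaches one half only under very large assumed effects.

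**Conclusion.** The gap is real and modest in size. SAP 14.2.2 permits logistic regression with Wald intervals at 6 participants in the rarer level and, in the visible text, has no provision for separation in a binary model. If the 6 is an overall count, about a quarter of trials at exactly that count would have an arm without events. For a given dose-placebo pair the chance is 16.6%. It is 8.3% for placebo, the case that makes both odds ratios infinite; an empty dose arm gives an odds ratio of 0 for that dose only.

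These figures rest on 50 analysed per arm, equal risk and no missing data. They do not apply to the three listed outcomes if the 6 is counted per arm. The deterioration analysis is a further loose end: if no minimum applies to it, the chance is 37% at 5 events and 55% at 4.

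This is a cheap improvement to exploratory secondary analyses. It does not affect the primary endpoint.

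**What to change.** In SAP 14.2.2:

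1. Fit the binary clinical-status models, including deterioration, by Firth's penalised likelihood with profile-likelihood 95% intervals, at least whenever the rarer level is sparse or an arm has no event. Using it throughout avoids a data-dependent switch and nearly coincides with ordinary logistic regression when events are ample.
2. State that treatment, corticosteroid use and country enter as main effects, in line with SAP section 7, in place of the reference to randomization strata.
3. State whether the minimum of 6 applies overall or per arm, and whether it covers the deterioration analysis.

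The cost is a few lines in the SAP and two options in the logistic program. The downside is slight shrinkage of large odds ratios when events are few. Intervals will still be wide at such counts, but they will be computable and fixed in advance.
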